9. MEASUREMENT OF EFFECT

Participants will be assessed by RECIST version 1.1 criteria. For the purposes of this study, participants should be reevaluated every 6 weeks. In addition to a baseline scan, confirmatory scans should also be obtained no sooner than 4 weeks and no later than 6 weeks following initial documentation of an objective response.

9.1 Antitumor Effect– Solid Tumors

Response and progression will be evaluated in this study using the new international criteria proposed by the Response Evaluation Criteria in Solid Tumors (RECIST) (Eisenhauer et al, 2009) guideline. Changes in the diameter (unidimensional measurement) of the tumor lesions are used in the RECIST criteria.

9.1.1 Definitions

Evaluable for toxicity. All participants who receive at least one dose of study treatment will be evaluable for toxicity from the time of their first treatment.

Evaluable for objective response. Only those participants who have measurable disease present at baseline, have received at least one cycle of therapy, and have had their disease re-evaluated will be considered evaluable for response. These participants will have their response classified according to the definitions stated below. (Note: Participants who exhibit objective disease progression or die prior to the end of cycle 1 will also be considered evaluable.)

9.1.2 Disease Parameters

Measurable disease. Measurable disease is the presence of at least one (1) lesion that can be accurately measured in at least one dimension with longest diameter ≥ 20 millimeters (mm) using conventional techniques (CT, MRI, x-ray) or ≥ 10 mm with spiral CT scan. Measurable lesions must be at least 2 times the slice thickness in mm. All tumor measurements must be recorded in millimeters (or decimal fractions of centimeters).

Note: A lesion in a previously irradiated area is not eligible for measurable disease unless there is objective evidence of progression of the lesion prior to study enrollment. Lesions in previously irradiated areas must be clearly identified as such.

Malignant lymph nodes. To be considered pathologically enlarged and measurable, a lymph node must be ≥ 15 mm in short axis when assessed by CT scan (CT scan slice thickness recommended to be no greater than 5 mm). At baseline and in follow-up, only the short axis will be measured and followed.

Non-measurable disease. All other lesions (or sites of disease), including small lesions (longest diameter < 10 mm or pathological lymph nodes with ≥ 10 to < 15 mm short axis), are considered non-measurable disease. Bone lesions, leptomeningeal disease, ascites, pleural/pericardial effusions, lymphangitis cutis/pulmonis, inflammatory breast disease, abdominal masses identified by physical exam that are not measurable by reproducible imaging techniques, and cystic lesions are all considered non-measurable.

CONFIDENTIAL

This document is confidential. Do not disclose or use except as authorized.

Target lesions. All measurable lesions up to a maximum of 2 lesions per organ and 5 lesions in total, representative of all involved organs, should be identified as target lesions and recorded and measured at baseline. Lesions must be accurately measured in 1 dimension with a minimum size of 10 mm by CT or MRI (slice thickness no greater than 5 mm), 20 mm by *chest* x-ray. Nodes must have a short axis \geq 15 mm. The short axis should be included in the sum of the lesions in the calculation of response. Nodes that shrink to $<$ 10 mm are considered normal. Target lesions should be selected on the basis of their size, be representative of all the involved organs, and should be lesions that can be followed with reproducible repeated measurements.

Lytic bone lesions or mixed lytic-blastic lesions, *with identifiable soft tissue components*, that can be evaluated by cross sectional imaging techniques such as CT or MRI can be considered target lesions if the *soft tissue component* meets the definition of measurability as defined above. Cystic lesions thought to represent cystic metastases can be considered as target lesions. However, if non-cystic lesions are present, these are preferred for selection as target lesions. Lesions in previously irradiated areas or areas subject to other loco-regional therapy are usually not considered measurable unless there has been demonstrated progression of that lesion.

Non-target lesions. All other lesions, including small lesions $<$ 10 mm or pathological lymph nodes measuring \geq 10 mm to $<$ 15 mm in short axis, as well as truly non-measurable lesions, which include leptomeningeal disease, ascites, pleural or pericardial effusion, inflammatory breast disease, lymphangitic involvement of skin or lung, abdominal masses identified by physical exam that are not measurable by reproducible imaging techniques.

9.1.3 Methods for Evaluation of Measurable Disease

All measurements should be taken and recorded in metric notation, using a ruler, calipers, or digital measurement tool. All baseline evaluations should be performed as closely as possible to the beginning of treatment and never more than 4 weeks before the beginning of the treatment.

The same method of assessment and the same technique should be used to characterize each identified and reported lesion at baseline and during follow-up. Imaging-based evaluation is preferred to evaluation by clinical examination when both methods have been used to assess the anti-tumor effect of a treatment.

Clinical lesions. Clinical lesions will only be considered measurable when they are superficial (e.g., skin nodules and palpable lymph nodes). For the case of skin lesions, documentation by color photography, including a ruler to estimate the size of the lesion, is recommended.

Conventional CT and MRI. These techniques should be performed with cuts of 10 mm or less in slice thickness contiguously. Spiral CT should be performed using a 5 mm contiguous reconstruction algorithm. This applies to tumors of the chest, abdomen, and pelvis. Head and neck tumors and those of extremities usually require specific protocols.

FDG PET and PET/CT. The acquisition of FDG PET and FDG PET/CT scans should follow the NCI Guidelines for using FDG PET as an indicator of therapeutic response (L.K. Shankar, J.M. Hoffman, S. Bacharach, M.M. Graham, J. Karp, A.A. Lammertsma, S. Larson, D.A. Mankoff, B.A. Siegel, A. Van den Abbeele, J. Yap, D. Sullivan. Consensus recommendations for the use of 18F-FDG PET as an indicator of therapeutic response in patients in National Cancer Institute Trials. J Nucl Med, 47(6):901-903, 2006). Participants should avoid strenuous exercise and be on a low carbohydrate diet for 24 hours prior to the scan. Participants should fast for 4 hours or longer prior to the FDG injection and should have a serum glucose of less than 200 mg/dL at the time of FDG injection. A 10-20 mCi dose of FDG should be injected for typical adult participants. For longitudinal studies with multiple scans, particular attention should be paid to ensure consistent participant preparation and acquisition parameters between the follow-up scan and the baseline scan. When designing a study where PET scans are going to be utilized as one of the modalities to evaluate efficacy, it is important to consult with physicians in nuclear medicine in designing the appropriate criteria to be utilized.

9.1.4 Response Criteria

Evaluation of Target Lesions

Complete Response (CR): Disappearance of all target lesions. Any pathological lymph node must have reduction in short axis to < 10 mm.

Partial Response (PR): At least a 30% decrease in the sum of the diameters of target lesions, taking as reference the baseline sum diameters.

Progressive Disease (PD): At least a 20% increase in the sum of the diameters of target lesions, taking as reference the smallest sum on study with at least a 5 mm absolute increase in the sum of all lesions. The appearance of one or more new lesions* denotes disease progression.

Stable Disease (SD): Neither sufficient shrinkage to qualify for PR nor sufficient increase to qualify for PD, taking as reference the smallest sum diameters while on study.

Unknown (UN): Assessment of target lesions cannot be made due to insufficient or unevaluable data. In this case, a concise explanation must be given.

Note: If tumor response data is missing for target lesions, the overall assessment must be UN unless there is new disease that would result in an overall assessment of PD. However, if there is missing or unevaluable data for non-target lesions, but data is available for all target lesions, the overall response for that time point will be assigned based on the sum LD of all target lesions. Additionally, the assessment of CR cannot be made if there is missing or unevaluable data for non-target lesions. In this case, the overall assessment would be PR.

***Definition of New Lesion:** The finding of a new lesion should be unequivocal (i.e. not due to difference in scanning technique, imaging modality, or findings thought to represent something other than tumor (ex: new bone lesions may be healing or flare of pre-existing lesions). However, a lesion identified on a follow-up scan in an anatomical location that was not scanned at baseline is considered new and will indicate PD. If a new lesion is equivocal (because of small size, etc.), follow-up evaluation will clarify if it truly represents new disease and if PD is confirmed, progression should be declared using the date of the initial scan on which the lesion was discovered.

Evaluation of Non-Target Lesions

Complete Response (CR): Disappearance of all non-target lesions and normalization of tumor marker level. All lymph nodes must be non-pathological in size (< 10 mm short axis).

Incomplete Response/Stable Disease (SD): Persistence of one or more non-target lesions and/or maintenance of tumor marker level above the normal limits.

Progressive Disease (PD): Appearance of one or more new lesions* (new lesions must be > slice thickness) and/or unequivocal progression of existing non-target lesions.

Overall level of substantial worsening that merits discontinuation of therapy. A useful test that can be applied when assessing non-targets for unequivocal progression is to consider if the increase in overall disease burden based on the change in non-measurable disease is comparable in magnitude to the increase that would be required to declare PD for measurable disease.

Unknown (UN): Assessment of non-target lesions cannot be made due to insufficient or unevaluable data. In this case, a concise explanation must be given.

***Definition of New Lesion:** The finding of a new lesion should be unequivocal (i.e. not due to difference in scanning technique, imaging modality, or findings thought to represent something other than tumor (ex: new bone lesions may be healing or flare of pre-existing lesions). However, a lesion identified on a follow-up scan in an anatomical location that was not scanned at baseline is considered new and will indicate PD. If a new lesion is equivocal (because of small size, etc.), follow-up evaluation will clarify if it truly represents new disease and if PD is confirmed, progression should be declared using the date of the initial scan on which the lesion was discovered.

Evaluation of Best Overall Response

The best overall response is the best response recorded from the start of the treatment until disease progression/recurrence (taking as reference for progressive disease the smallest measurements recorded since the treatment started). The participant's best response assignment will depend on the achievement of both measurement and confirmation criteria.

For Participants with Measurable Disease (i.e., Target Disease)

Target Lesions	Non-Target Lesions	New Lesions	Overall Response	Best Overall Response for when Confirmation is Required:
CR	CR	No	CR	≥4 wks confirmation
CR	Non-CR/Non-PD	No	PR	≥4 wks confirmation
CR	Not evaluated	No	PR	
PR	Non-CR/Non-PD/Not evaluated	No	PR	
SD	Non-CR/Non-PD/Not evaluated	No	SD	Documented at least once ≥4 wks from baseline
PD	Any	Yes or No	PD	No prior SD, PR or CR
Any	PD*	Yes or No	PD	
Any	Any	Yes	PD	

* In exceptional circumstances, unequivocal progression in non-target lesions may be accepted as disease progression.
 
Note: Participants with a global deterioration of health status requiring discontinuation of treatment without objective evidence of disease progression at that time should be reported as "symptomatic deterioration". Every effort should be made to document the objective progression even after discontinuation of treatment.
				

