5.6 Follow-up Assessments and Study Completion

After discontinuation of study drug treatment, participants will continue to be evaluated for safety and survival data. The following visits will be performed:

28 Day Safety Visit: All participants will have a follow-up visit scheduled 28 days (± 7 days) after the last dose of study treatment to follow-up for AEs and SAEs. AEs and SAEs that are still ongoing at the time of discontinuation and considered as related to study treatment will continue to be followed weekly until resolution, stabilization of condition, or end of study.

Treatment Follow-up Period: Any participant who is discontinued from study treatment for any reason other than disease progression will continue to have tumor assessments every 12 weeks until progression, death or until a new anti-neoplastic therapy is initiated. The investigator, or his/her designee, will continue to collect information until the first initiation of additional anti-neoplastic therapies for each discontinued participant until one year following last participant last visit.

All participants who have progressed during study treatment or during the Treatment Follow-up Period will be followed every 12 weeks for survival up to 1 year after the last participant is discontinued from the study.

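### Section 9.1.4 scores one kind of scan both UN and PD: target data missing, existing non-target disease unequivocally worse, no new lesion (minor)

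*Combined protocol and SAP*

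**What the plan says.** All the scoring rules sit in protocol section 9.1.4.

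- **Missing-data note, under target lesions.** When a scan lacks target-lesion data, the note says that "the overall assessment must be UN unless there is new disease that would result in an overall assessment of PD". The rule is mandatory and has one exception. The UN category just above it covers the case where "Assessment of target lesions cannot be made due to insufficient or unevaluable data".
- **Non-target progression.** PD is the appearance of new lesions "and/or unequivocal progression of existing non-target lesions". The text then explains how substantial the worsening must be, with a comparison to the growth in burden needed for measurable disease.
- **Best-overall-response table.** One row reads: target Any, non-target PD (with an asterisk), new lesions Yes or No, overall response PD.
- **Footnote to that asterisk.** "In exceptional circumstances, unequivocal progression in non-target lesions may be accepted as disease progression".

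Elsewhere, PFS runs to objective progression or death (9.1.6), or to first documented progression or death (13.3). Section 13.3 makes all secondary endpoints exploratory. Scans are every 6 weeks on treatment (section 9). After treatment stops, section 5.6 states: "Any participant who is discontinued from study treatment for any reason other than disease progression will continue to have tumor assessments every 12 weeks". Sections 5 and 5.5 end that scanning when another anticancer treatment starts. Section 8.1.2 assigns RECIST scoring to a central imaging core whose reads need not guide clinical decisions in real time.

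**The concern.** A participant whose target lesions cannot be assessed, but whose existing effusion or other non-target disease has clearly worsened, gets a different overall code depending on which paragraph the reader applies. The code matters because PFS needs a documented or objective progression, and the documents give no PFS rule for UN assessments and no PFS censoring rule. Coding UN where PD was warranted can postpone or remove a progression date but never bring one forward, so any effect is towards longer PFS. In an open-label single-arm trial of 20, it is better that this choice is not left until results are visible.

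**Working it through.** **1. Put the rules side by side.** The test scan has missing target-lesion data, unequivocal progression of existing non-target lesions, and no new lesion.

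| Rule in 9.1.4 | Result |
|---|---|
| Missing-data note | UN (exception not met) |
| Non-target PD definition | PD |
| Table row Any / PD* / Yes or No | PD |
| Footnote to PD* | PD permitted, not required |

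**2. Check whether the note's exception could cover the scan.** The section uses the term new disease when defining a new lesion: if a lesion is equivocal, "follow-up evaluation will clarify if it truly represents new disease". The term therefore means new lesions, not growth of existing ones, and the exception does not apply.

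**3. Check whether the table covers missing target data.** The table has no explicit row for an unknown target status, so the conflict rests on the plain meaning of Any. Even with the permissive footnote, the note forbids PD where the table and footnote allow it. No text ranks one above the other.

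**4. Check the primary endpoint.** The plan's rule in 13.1 is at least 4 responses in 20. The exact binomial tail gives power P(X ≥ 4 | n = 20, p = 0.30) = 0.8929 (stated 89%) and type I error P(X ≥ 4 | n = 20, p = 0.10) = 0.1330 (stated 13%). Both reproduce. UN and PD are both non-responses at that scan, so neither figure changes. One narrow link remains: best response is counted up to progression, so a UN leaves open a window that a PD would close.

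**5. Size when the next scan resolves the UN (the usual case).** The progression date moves by about 6 weeks on treatment or 12 weeks off it. If all 20 dates are observed, one such case shifts their mean by 6/20 = 0.3 weeks or 12/20 = 0.6 weeks.

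**6. Size when the progression is never recorded.** The documents give no rate, so this is an illustration. Assume exponential times, an event for every other participant, and censoring of the lost ones at the UN scan. With total follow-up T, estimated median = ln 2 × T / events. Losing k of 20 events leaves T unchanged, so the median is multiplied by 20/(20 − k) = 1/(1 − k/20):

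- k = 1: 20/19 = 1.05
- k = 2: 20/18 = 1.11

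If the event is instead counted at a later death, the factor depends on post-progression survival, which the documents do not give. With an assumed true median PFS of 3 months and an assumed post-progression median of 8 months, a simulation with 10% of progressions lost gave 3.34 months under censoring (3.34/3 = 1.11) and 3.42 months with the event at death (3.42/3 = 1.14).

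**The case against.** The strongest reply is that the follow-up rules repair most of these cases.

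- If the scan is UN and treatment continues, another scan follows in 6 weeks.
- If treatment stops without recorded progression, the participant belongs to the group scanned every 12 weeks. Section 5.5 also requires an end-of-study scan if the last was 4 or more weeks earlier.
- If treatment stops because progression was recorded, the first-documented-progression wording in 13.3 is arguably met.

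This largely stands. Complete loss needs a further step. One is that new anticancer therapy starts before the next scan. The other is that the investigator stops treatment for progression while the central read, following the note, is UN; scheduled off-treatment scans are then not specified. Section 8.1.2 makes such a split possible. The instruction at the end of 9.1.4 to keep trying to document progression concerns symptomatic deterioration without objective evidence, so it does not squarely cover this case.

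It can also be said that PFS is tied to objective progression and not to the overall code. That is fair, but no text says how a UN scan with clear non-target progression enters PFS.

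A reader might infer that the footnote is a second contradiction. The documents support that only weakly. The non-target definition already sets a demanding standard, with its own burden test, and a footnote reserving such calls for exceptional circumstances is broadly compatible with it.

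**Conclusion.** The conflict is real, is in the current text, and is confined to one kind of scan. Its usual effect is a PFS date one scan late; its occasional effect is a lost progression. The direction is towards longer PFS.

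A reader might infer that real progressions will routinely drop out of PFS, or that median PFS will be inflated by some 10% to 25%. The documents do not support either reading. They give no frequency for such scans. The case needs missing targets, unequivocal non-target worsening and no new lesion together, which is probably uncommon given the requirements for measurable disease and consistent imaging technique. The factors 1.05 and 1.11 assume exponential times and permanent loss to censoring of one or two of 20 progressions, so they are high-end illustrations and not expected effects.

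PFS is exploratory and no PFS threshold drives a decision. The 4-of-20 rule keeps its stated power and type I error. An earlier qualifying SD still counts towards DCR. Severity: minor.

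**What to change.** Reword the exception in the 9.1.4 note, for example: *UN, unless there is new disease or unequivocal progression of existing non-target lesions (as defined below), in which case the overall assessment is PD.* The note then agrees with the Any / PD* row and the non-target PD definition.

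Rewriting the footnote is optional; a cross-reference to the burden test in the non-target PD paragraph is enough.

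The cost is one edited clause in a protocol amendment, with no new data or scans. Reported PFS may read slightly shorter if such scans occur.

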9.1.5 Duration of Response

Duration of overall response: The duration of overall response is measured from the time measurement criteria are met for CR or PR (whichever is first recorded) until the first date that recurrence or PD is objectively documented, taking as reference for PD the smallest measurements recorded since the treatment started.

Duration of overall complete response: The duration of overall CR is measured from the time measurement criteria are first met for CR until the first date that recurrent disease is objectively documented.

Duration of stable disease: Stable disease is measured from the start of the treatment until the criteria for progression are met, taking as reference the smallest measurements recorded since the treatment started.

9.1.6 Progression-Free Survival

Progression-Free Survival (PFS) is defined as the duration of time from study enrollment to time of objective disease progression or death from any cause.

10. ADVERSE EVENT REPORTING REQUIREMENTS

10.1 Definitions

10.1.1 Adverse Event (AE)

CONFIDENTIAL

This document is confidential. Do not disclose or use except as authorized.

An adverse event (AE) is any undesirable sign, symptom or medical condition or experience that develops or worsens in severity after starting the first dose of study treatment or any procedure specified in the protocol, even if the event is not considered to be related to the study.

Abnormal laboratory values or diagnostic test results constitute adverse events only if they induce clinical signs or symptoms or require treatment or further diagnostic tests.

10.1.2 Serious adverse event (SAE)

A serious adverse event (SAE) is any adverse event, occurring at any dose and regardless of causality that:

- Results in death
- Is life-threatening. Life-threatening means that the person was at immediate risk of death from the reaction as it occurred, i.e., it does not include a reaction which hypothetically might have caused death had it occurred in a more severe form.
- Requires or prolongs inpatient hospitalization (i.e., the event required at least a 24-hour hospitalization or prolonged a hospitalization beyond the expected length of stay). Hospitalization admissions and/or surgical operations scheduled to occur during the study period, but planned prior to study entry are not considered SAEs if the illness or disease existed before the person was enrolled in the trial, provided that it did not deteriorate in an unexpected manner during the trial (e.g., surgery performed earlier than planned).
- Results in persistent or significant disability/incapacity. Disability is defined as a substantial disruption of a person's ability to conduct normal life functions.
- Is a congenital anomaly or birth defect; or
- Is an important medical event when, based upon appropriate medical judgment, it may jeopardize the participant and require medical or surgical intervention to prevent one of the outcomes listed above. Examples of such medical events include allergic bronchospasm requiring intensive treatment in an emergency room or at home; blood dyscrasias or convulsions that do not result in inpatient hospitalization, or the development of drug dependency or drug abuse.

Events **not** considered to be serious adverse events are hospitalizations for:

- routine treatment or monitoring of the studied indication, not associated with any deterioration in condition, or for elective procedures
- elective or pre-planned treatment for a pre-existing condition that did not worsen
- emergency outpatient treatment for an event not fulfilling the serious criteria outlined above and not resulting in inpatient admission
- respite care

CONFIDENTIAL

This document is confidential. Do not disclose or use except as authorized.

